Similarly, we will assess the interaction between driving pressure and 3 specific factors on the primary outcome: (1) supraglottic air way devices (i.e., LMAs) vs endotracheal tubes, (2) laparoscopic cases vs non-laparoscopic, and (3) craniotomy vs non-craniotomy cases. A significant interaction term will indicate that the relationship between driving pressure and the outcome is modified by these specific factors. Subsequent subgroup analyses will be performed in each subgroup to identify the impact of driving pressure specifically within each subgroup (i.e., driving pressure has a much larger impact on 30-day mortality among craniotomy cases than those observed among non-craniotomy cases). As a sensitivity analysis, we will also perform the primary analysis after exclusion of emergency surgery cases.

Secondary outcomes include postoperative pulmonary complications (PPCs) within 30 days (presence of class 1, 2, or 3) and length of stay. PPCs will be analyzed using multivariable logistic regression, while length of stay will utilize Poisson regression. All models will include driving pressure as the variable of interest, adjusting for the same factors as in the primary analyses. As above, we will assess the interaction between driving pressure and tidal volume to investigate the presence of modification of the relationship between tidal volume and the outcome by the driving pressure.

The primary exposure variable (driving pressure) is defined as the median of patient driving pressure values collected intraoperatively. In an exploratory manner, we plan to investigate other methods to quantify driving pressure that is informative of the outcome and can provide clinical relevance. One alternative is to utilize the cumulative number of minutes with a driving pressure over 15 cmH₂O, based

on findings in acute respiratory distress syndrome patients.⁴ Another alternative is to consider the area under the curve (of the continuously measured driving pressure) for each patient.

Power analysis

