Ventilation Mode	Ventilation mode	String	Concept 3182 Ventilator Mode (most common for case)
Intubation Time	First Intubation time (as minutes)	Integer	Concept 50695 Categorized note Intubation

	from anesthesia start)		
Extubation Time	Last Extubation Time	Integer	Concept 50202 – Emergence Patient Extubated
Reversal Time	Time of administration of NMB reversal	Integer	Concept 10739 – Sugammadex Concept 10315 – Neostigmine Concept 10383 – Pyridostigmine
Median tidal volume	Median TV	Integer	Concept 3190 – Tidal Volume Actual
Median respiratory rate	Median respiratory rate	Integer	Concept 3580 – RR
Median peak inspiratory pressure	Median peak inspiratory pressure	Integer	Concept 3185 – PIP
Median plateau inspiratory pressure	Median plateau inspiratory pressure	Integer	Concept 3186 – Plateau IP
Median PEEP	Median Positive End Expiratory Pressure	Integer	Concept 3210 – PEEP Measured
Median EtCO ₂	Median end tidal carbon dioxide	Integer	Concept 3235 – EtCO ₂ (mmHg)
Median FiO ₂	Median Fraction of Inspired Oxygen	Integer	Concept 3200 – Ventilator FiO ₂ Measured
Mortality (days)	Days from Date of Surgery to Date of Death	Integer	Mortality Table
Pulmonary Complications	See Appendix for ICD Diagnosis codes associated with Pulmonary Complications		

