Appendix: ICD Diagnosis Codes Associated with Pulmonary Complications

Based on Douville study under review for publication.

Class 1 Pulmonary Complications

514	Pulmonary congestion and hypostasis
518.7	Transfusion related lung injury (TRALI)
997.3	Respiratory complications not elsewhere classified
997.31	Ventilator associated pneumonia
997.32	Postprocedural aspiration pneumonia
997.39	Other respiratory complications
J95.84	Transfusion related lung injury (TRALI)
J95.851	Ventilator associated pneumonia
J98.9	Respiratory disorder, unspecified
J95.859	Other complication of respirator
J95.88	Other intraoperative complications of respiratory system, not elsewhere classified
J95.89	Other postprocedural complications and disorders of respiratory system, not elsewhere classified

Class 2 Pulmonary Complications

480*	Viral pneumonia
481*	Pneumococcal pneumonia
482*	Other bacterial pneumonia
483*	Pneumonia due to other specified organisms
484*	Pneumonia in infectious diseases classified elsewhere
485*	Bronchopneumonia, organism unspecified
486*	Pneumonia, organism unspecified
506	Respiratory conditions due to chemical fumes and vapors
506.1	Acute pulmonary edema due to fumes and vapors
506.2	Upper respiratory inflammation due to fumes and vapors
506.3	Other acute and subacute respiratory conditions due to fumes and vapors
507*	Pneumonitis due to solids and liquids
512*	Pneumothorax and air leak
518.1	Nontraumatic subcutaneous emphysema
518.4	Acute edema of the lung, unspecified
518.5	Pulmonary insufficiency following trauma and surgery
518.51	Acute respiratory failure following trauma and surgery
518.52	Other pulmonary insufficiency, not elsewhere classified, following trauma and surgery
518.53	Acute and chronic respiratory failure following trauma and surgery
518.81	Acute respiratory failure
518.82	Other pulmonary insufficiency, not elsewhere classified
786.09	Respiratory Insufficiency
799.1	Respiratory arrest
J12*	Viral pneumonia, not elsewhere classified
J13*	Pneumonia due to Streptococcus pneumoniae
J14*	Pneumonia due to Hemophilus influenzae

J15* Bacteria pneumonia, not elsewhere classified
 J16* Pneumonia due to other infectious organisms, not elsewhere classified
 J17 Pneumoniae in diseases classified elsewhere
 J18* Pneumonia, unspecified organism
 J68.0 Bronchitis and pneumonitis due to chemicals, gases, fumes and vapors
 J68.1 Pulmonary edema due to chemicals, gases, fumes, and vapors

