 J68.2 Upper respiratory inflammation due to chemicals, gases, fumes, and vapors, not elsewhere classified
 J68.3 Other acute and subacute respiratory conditions due to chemicals, gases, fumes, and vapors
 J68.4 Chronic respiratory conditions due to chemicals, gases, fumes, and vapors
 J68.8 Other respiratory conditions due to chemicals, gases, fumes, and vapors
 J68.9 Unspecified respiratory conditions due to chemicals, gases, fumes, and vapors
 J85.1 Abscess of lung with pneumonia
 J69.0 Pneumonitis due to inhalation of food and vomit
 J80 Acute respiratory distress syndrome
 J81.0 Acute pulmonary edema
 J93* Pneumothorax and air leak
 J95.811 Postprocedural pneumothorax
 J95.812 Postprocedural air leak
 J95.821 Acute postprocedural respiratory failure
 J95.822 Acute and chronic postprocedural respiratory failure
 J96.0 Acute respiratory failure
 J96.00 Acute respiratory failure, unspecified whether with hypoxia or hypercapnia
 J96.01 Acute respiratory failure with hypoxia
 J96.02 Acute respiratory failure with hypercapnia
 J96.1 Chronic respiratory failure
 J96.10 Chronic respiratory failure, unspecified whether with hypoxia or hypercapnia
 J96.11 Chronic respiratory failure, with hypoxia
 J96.12 Chronic respiratory failure, with hypercapnia
 J96.2 Acute and chronic respiratory failure following trauma and surgery
 J96.20 Acute and chronic respiratory failure unspecified whether with hypoxia or hypercapnia
 J96.21 Acute and chronic respiratory failure with hypoxia
 J96.22 Acute and chronic respiratory failure with hypercapnia
 J96.9 Respiratory failure, unspecified
 J96.90 Respiratory failure, unspecified whether with hypoxia or hypercapnia
 J96.91 Respiratory failure, unspecified with hypoxia
 J96.92 Respiratory failure, unspecified with hypercapnia
 R09.0 Asphyxia and hypoxemia
 R09.01 Asphyxia
 R09.02 Hypoxemia
 R09.2 Respiratory arrest
 S27.0 Traumatic pneumothorax

Class 3 Pulmonary Complications

415.1 Pulmonary embolism and infarction
 415.11 Iatrogenic pulmonary embolism and infarction
 415.12 Septic pulmonary embolism

415.19 Other pulmonary embolism and infarction
415.3 Pulmonary embolism and infarction, episode of care unspecified
487* Influenza
488* Influenza due to certain identified influenza viruses
799* Cerebral asphyxia/suffocation/asphyxia/hypoxia
998.81 Surgical subcutaneous emphysema
958.7 Traumatic subcutaneous emphysema
I26.0 Pulmonary embolism with acute cor pulmonale
I26.01 Septic pulmonary embolism with acute cor pulmonale

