I26.02 Saddle embolus of pulmonary artery with acute cor pulmonale
I26.09 Other pulmonary embolism with acute cor pulmonale
I26.9 Pulmonary embolism without acute cor pulmonale
I26.90 Septic pulmonary embolism without acute cor pulmonale
J09* Influenza due to certain identified influenza viruses
J10* Influenza due to other identified influenza virus
J11* Influenza due to unidentified influenza virus
R06.4 Hyperventilation
R09.1 Pleurisy
R09.3 Abnormal sputum
R09.8 Other specified symptoms and signs involving the circulatory and respiratory systems
T79.7 Traumatic subcutaneous emphysema

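### The PPC code list counts chronic respiratory failure and chronic chemical lung conditions as postoperative complications, so this secondary outcome is misclassified

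*Protocol*

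**What the plan says.** The Statistical analysis section of the protocol defines the outcome as "postoperative pulmonary complications (PPCs) within 30 days (presence of class 1, 2, or 3"), to be analysed by multivariable logistic regression on driving pressure with the covariates of the primary model. One qualifying code is enough to make a patient a case.

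The appendix of ICD diagnosis codes lists, under Class 2, "J96.1 Chronic respiratory failure" together with J96.10, J96.11 ("J96.11 Chronic respiratory failure, with hypoxia") and J96.12. It also lists "J68.4 Chronic respiratory conditions due to chemicals, gases, fumes, and vapors".

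The Secondary outcomes section says the classes sort complications by how likely they are to stem from ventilator management. In the table of variables to be collected, the PPC row says only "See Appendix for ICD Diagnosis codes associated with Pulmonary Complications". The same table records chronic pulmonary disease as one Boolean taken from billing diagnoses. The Introduction defines driving pressure as tidal volume over respiratory-system compliance.

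**The concern.** A condition coded as chronic, with no acute component, is ordinarily present before the patient reaches the operating room. It cannot then be a consequence of intraoperative ventilation, and it does not fit the stated purpose of the classes. Counting it as an event adds cases whose onset precedes the exposure.

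This could do more than add noise. Driving pressure depends on compliance, so if patients with these codes have stiffer or more compliant lungs than the rest, their exposure differs systematically. The PPC model could then show an association that reflects baseline lung disease and not ventilation. The limitations section of the protocol worries about a result that shows only that sick patients do worse; these codes invite that reading for the PPC outcome.

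**Working it through.** **1. The code list against the outcome rule.**

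- Chronic entries in Class 2: J96.1, J96.10, J96.11, J96.12 and J68.4.
- Acute-on-chronic failure has its own entries (J95.822, J96.2, J96.20 to J96.22), and acute failure has J95.821 and J96.0 to J96.02. A patient with an acute event so coded is counted without the chronic codes.
- The printed ICD-9 entries for respiratory failure are acute (518.51, 518.81) or acute and chronic (518.53). None is purely chronic. The two code systems therefore differ on this point.
- The 30-day window limits when a code counts, not when the disease began.

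**2. The plan's own benchmark.** The documents give no figure for PPC. The only power figure concerns mortality: effect size 0.049 (log odds per SD), N = 85,000, event rate 10%, R² = 0.3, alpha 0.05, power 95%. By the Hsieh formula:

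(1.960 + 1.645) / √(85,000 × 0.10 × 0.90 × 0.70) = 3.605 / √5,355 = 0.0493.

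This reproduces the stated value. It serves below only as a yardstick.

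**3. A simple illustration. All rates are assumed.** New PPC 5% in both halves of driving pressure; chronic codes in 1% overall and twice as common in the upper half (1.33% v 0.67%); 42,500 patients per half.

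- Counted events: 6.33% v 5.67%.
- Odds ratio = (0.0633/0.9367) / (0.0567/0.9433) = 0.0676/0.0601 = 1.12.
- SE(log OR) = √(1/(42,500 × 0.0633 × 0.9367) + 1/(42,500 × 0.0567 × 0.9433)) = 0.029, so z = 0.117/0.029, about 4.
- Share of counted events that are chronic: 1/(5 + 1), one in six. This is an upper figure, since a chronic-coded patient with a new PPC would count anyway.
- If the chronic codes are twice as common in the lower half instead, the odds ratio is 1/1.12 = 0.89.

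With chronic codes at 0.25 to 2%, new PPC at 5 to 10% and an upper-to-lower ratio of 1.25 to 2, the null-effect odds ratio runs from 1.01 to 1.23. With a ratio of 0.5 it runs from 0.81 to 0.98.

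**4. Continuous driving pressure with the yes/no flag.** Simulated logistic regression, 1,000,000 patients per scenario, no true effect on new PPC, every chronic-coded patient counted as a case. Assumed: the flag captures 50% or 80% of chronic-coded patients and 15% of the others.

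| Chronic-coded | Shift in driving pressure | New PPC | Log OR per SD, crude | Adjusted for flag | Chronic-coded patients removed |
|---|---|---|---|---|---|
| 0.5% | 0.25 SD | 10% | 0.005 to 0.011 | 0.005 to 0.011 | -0.007 to 0.001 |
| 1% | 0.5 SD | 10% | 0.045 to 0.046 | 0.045 | -0.002 to 0.000 |
| 1% | 0.5 SD | 5% | 0.082 to 0.083 | 0.080 to 0.082 | -0.003 to -0.001 |
| 2% | 1.0 SD | 5% | 0.278 to 0.282 | 0.263 to 0.277 | -0.005 |

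The adjusted odds ratio per SD spans about 1.01 to 1.32. The middle case with 10% new PPC, 0.045, is about the size of the 0.049 yardstick. Removing chronic-coded patients brings the estimate back to zero within simulation noise (about ±0.01).

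The flag does little here because it does not isolate the chronic-coded patients. At 1% prevalence and 80% capture, they make up 0.008/(0.008 + 0.99 × 0.15) = 5% of flagged patients, so the imbalance persists within the flagged group.

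**The case against.** Several stronger readings are tempting, and the documents do not support them.

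- *That the codes create a positive association by definition.* This needs chronic-coded patients to have higher driving pressure. No section establishes that. The protocol says only that driving pressure will presumably differ between healthy, emphysematous and obstructed lungs, without giving a direction. Lungs with high compliance would push the estimate the other way.
- *That the lack of a present-on-admission or onset rule is itself an error.* The protocol does state a postoperative 30-day window. How that window is applied to billing codes is operational detail that an analysis plan not shown here, or the study from which the list is taken, may supply. The explicit naming of chronic disease as an event is different: a filter would have to override the printed list.
- *That non-septic pulmonary embolism is lost in ICD-10.* The parent I26.9 is listed, and its label covers embolism without acute cor pulmonale. The appendix does not say whether an unstarred parent code matches its subcodes, so no gap is shown.
- *That the coding switch biases the result.* No study dates are given, and nothing shows that driving pressure changed with coding era. Year of service is collected, and the confounder list is open-ended, so adjustment for year is already allowed.

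The objections to the numbers also stand in part. All rates are assumed. The two-halves calculation is unadjusted, and the simulation adjusts only for the flag, not for ASA score or BMI, so it does not show what the full planned model would leave. Excluding tracheostomy and in-situ tubes removes some patients with chronic failure. The protocol also concedes that PPC reporting varies between institutions, which is one reason it made mortality primary.

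None of this answers the central fact that five chronic codes are printed as postoperative events.

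**Conclusion.** The point holds for the code list. As written, a patient with only J96.1, J96.10, J96.11, J96.12 or J68.4 is a PPC case, although the condition ordinarily precedes surgery. The misclassification follows from the text alone, apart from that clinical premise about chronic conditions.

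Bias in the driving-pressure association is possible but not established. Its sign depends on the compliance of chronic-coded patients, and its size on how common the codes are; the documents give neither. Under the assumptions shown, the null-effect odds ratio lies between about 1.01, which is negligible, and 1.3 if these patients have higher driving pressure, and below 1 if lower. The single pulmonary disease flag may remove only part of it.

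Only the secondary PPC outcome is affected. The change should be made, but the primary mortality analysis does not depend on it.

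**What to change.** Remove J96.1, J96.10, J96.11, J96.12 and J68.4 from the PPC outcome. Where they are recorded before or at admission, use them as baseline covariates in the PPC model. Keep the acute and acute-on-chronic codes. Where diagnosis dates or present-on-admission flags exist, count the remaining codes only if new after surgery, with the same rule for ICD-9 and ICD-10. If the authors wish to keep the chronic codes, they should state why these represent postoperative events.

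The data are retrospective, so the list edit costs little and gives slightly fewer PPC events. The onset rule depends on data fields that the variable table does not list, so their availability must be checked first; removing the five codes does not depend on it.

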Appendix: Inhaled Steroids and Tradenames

Beclomethasone	QVAR, Beconase Aq, Becotide, Beclocort
Flunisolide	Aerospan
Fluticasone	Flovent, Advair Diskus, Arnuity Ellipta
Budesonide	Pulmicort
Fluticasone-salmeterol	Advair HFA
Budesonide-formoterol	Symbicort
Mometasone	Asmanex
Ciclesonide	Alvesco, Zetonna
Formoterol-mometasone	Dulera
Fluticasone-vilanterol	Breo Ellipta, Relvar Ellipta
fluticasone/umeclidinium/vilanterol	Trelegy Ellipta

Handling of missing data and artifacts

Patterns of missingness will be summarized. We expect low proportion of missing data in the primary endpoint as it is one that is clearly defined and conventionally reported. Similarly, we expect low missingness in intraoperative measures. We will investigate whether the missingness is missing completely at random or missing at random. In the absence of informative missingness, we will proceed with complete-case analyses. Otherwise, multiple imputation will be performed.

Medians will be used to summarize tidal volume and pressure data. Zero value artifacts will be removed. For tidal volumes we will remove values less than 2 mL/kg and more than 20 mL/kg. Only values between intubation and extubation will be used in these medians.

Areas for discussion/known limitations

- Alternative methods for selecting a patient's index case are:
 - First surgery for patient (current proposal)
 - Remove all patients with repeat surgeries
 - Surgery with longest ventilator duration (maximum exposure)
 - First surgery during admission or 30-day period (possibly multiple cases per patient, if multiple admissions)
 - Surgery with highest anesthesia CPT base unit value
- There will be selection bias since not all locations report all the included data.
- We will exclude one-lung ventilation patient group since they may represent a significantly different patient population and pulmonary physiology. Why not focus on sicker patients?
 - Our study focuses on the noncardiac surgery patient population in general and assumes ventilatory management can have impact on patients 30-day mortality. While the broadness of our study is a strength, it also introduces a possibility that a signal may be drowned in the noise of its large, heterogenous patient population. Focusing on only high-risk groups opens the criticism that finding a correlation will only show that “sick patients are more likely to be sicker.”

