PCRC PROPOSAL COVER SHEET

Title of Study or Project:	Association Between Driving Pressure and Postoperative Outcomes in Non-Cardiac Surgery Patients
Primary Institution:	Memorial Sloan Kettering Cancer Center, New York, NY
Principal Investigator:	[name]
Co-Investigators:	[name] [name] [name] [name]
Type of Study:	 Exploratory  Retrospective Observational  Prospective Randomized
IRB Number/Status:	Approved, IRB Exempt Protocol X18-028
Hypothesis:	Increased driving pressure during nonspontaneous mechanical ventilation will correlate with increased 30-day in-hospital mortality in a noncardiac surgery population
Number of Patients/Participants:	Estimated 85,000. (DataDirect query found 128,489 patients with 144,876 cases, and we estimate 1/3 loss of cases due to insufficient data.)
Power Analysis:	The primary hypothesis of interest is the effect of driving pressure in the presence of other covariates using multivariable logistic regression. We assume squared multiple correlation coefficient (R^2) of 0.3 to generate the variance inflation factor. Assuming an alpha of 0.05 and 10% event rate, an anticipated sample size of 85,000 will provide 95% power to detect an effect size of 0.049.
Proposed statistical test/analysis:	Multivariate logistic regression will be performed using the postoperative outcome of 30-day in-hospital mortality and driving pressure as the exposure to determine if an association exists. Secondary outcome analysis will focus on pulmonary complications defined by ICD 9/10 Codes. Variables including but not limited to age, gender, intubation time length, pulmonary disease, BMI, and ASA score will be analyzed.
Resources (Brief summary of resources for data collection, personnel, financial):	The MPOG database will be queried for the specified concept IDs with programmatic support from the MPOG Coordinating Center. Statistical analyses will be performed by biostatisticians from the MSKCC Department of Epidemiology & Biostatistics led by [name].

Introduction

What is the significance of the clinical problem being addressed?

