- 1) Investigate the association of driving pressure and 30-day in-hospital mortality in nonspontaneous mechanically ventilated non-cardiac surgical patients undergoing two lung ventilation.
- 2) Investigate the association of tidal volume in mL per kg IBW with 30 day in-hospital mortality and how this relationship is modified by driving pressure
- 3) Subgroup analysis: There are several patient subgroups that may play a role in modifying the association between driving pressure and mortality:
 - Pulmonary pressure using supraglottic airway devices (i.e. LMA's) may not be identical to endotracheal tubes given that the physiology is slightly different. We will analyze these two groups to determine if how the association to outcomes are modified.
 - Laparoscopic cases have increased extra-thoracic pressures on the lung due to insufflation which may not be analogous to increased pulmonary pressures due to ventilatory strategies.
 - Craniotomy cases sometimes are managed with hyperventilatory strategies to decrease intracranial pressures through hypocapnia. These hyperventilatory strategies may cause increased pulmonary pressure that is different from other types of cases and should be examined separately.
- 2) Secondary objective: Investigate the association of driving pressure and postoperative pulmonary complications within 30 days (presence of class 1, 2, or 3), and also length of stay.

Methods

Study Database and Population

MPOG is a non-profit academic consortium analyzing perioperative outcomes from hospitals in 18 states and 2 countries. Using electronic records including over 8.2 million anesthetic cases, MPOG facilitates analysis of the critical factors we are investigating regarding intraoperative respiratory variables and postoperative outcomes.

IRB statement

The project has been approved by the Memorial Sloan Kettering Cancer Center IRB under protocol X18-028.

Exposure Variables

- **Case Start:**
 1. Anesthesia Induction End (Concept 50005). If not available, then
 2. Anesthesia Induction Begin (Concept 50004). If not available, then
 3. Procedure Start (Concept 50006). If not available, then
 4. Patient in Room (Concept 50003). If not available, then
 5. Anesthesia Start (Concept 50002).
- **Case End:**
 1. Patient Extubated (Concept 50202). If not available, then
 2. Procedure End (Concept 50007). If not available, then
 3. Patient Out of Room (Concept 50008). If not available, then
 4. Anesthesia End (Concept 50009).

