- Patients with a tracheostomy (in-situ or new) or in-situ endotracheal tube (Concept 50671). Supraglottic airways will be included in the study but examined more closely with secondary statistical analysis as described below.
- Patients with single-lung ventilation will be excluded
- Patients with presence of a double-lumen endotracheal tube or presence of bronchial blocker will be excluded
- Cardiac operations will be excluded
 - Anesthesia CPTs 00560, 00561, 00562, 00563, 00566, 00567, 00580
- All cases with cardiopulmonary bypass will be excluded
 - 50399 Cardiopulmonary bypass - aortic clamp on/off note
 - 50409 Cardiopulmonary bypass terminated
 - 50410 Cardiopulmonary bypass initiated (full)
 - 50416 Cardiopulmonary bypass - crossclamp and circulatory arrest time totals
 - 50417 Cardiopulmonary bypass - Access cannula removed note
 - 50714 Cardiopulmonary bypass - Bypass start / stop event
- Cases performed by cardiac surgical service (Concept 80005)
- Lung and liver transplant surgery will be excluded since they have unique pathophysiology to influence pulmonary complications:
 - Anesthesia CPT 00796 (liver), 00580 (lung)
- Highest base unit value of Anesthesia CPT is 3 or less.

Data source

An MPOG DataDirect query for cases meeting recording plateau pressure found 128,489 patients with 144,876 cases. We estimate 1/3 loss of cases due to insufficient data, so we expect approximately 85,000 patients with measured plateau pressure.

Statistical analysis

All patient demographic and clinical factors will be summarized using Number (%) and median (25th, 75th percentile) or mean (standard deviation) where appropriate. Summaries may be stratified by quantiles of driving pressure.

In the primary analyses, driving pressure will be recorded as the median of patient trajectory. The correlation between driving pressure and other ventilatory parameters (tidal volume, PEEP, plateau pressure etc.) will be quantified by the Spearman correlation coefficients.

The primary outcome is 30-day in-hospital mortality from the date of surgery, recorded as a binary outcome. Since MPOG data does not reliably have out of hospital mortality, we will assume mortality is only recorded in-hospital.

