The primary exposure is driving pressure, recorded as the median of patient trajectory (continuous variable). The relationship between driving pressure and 30-day in-hospital mortality will be assessed with a multivariable logistic regression model, adjusting for preoperative and intraoperative factors. Confounders include but are not limited to age at surgery, gender, intubation time, ventilatory mode, airway device (i.e. endotracheal tube, LMA), pulmonary disease, BMI, ASA score. Potential non-linear relationship between driving pressure and the outcome will be examined using restricted cubic spline analysis. If a significant non-linear relationship between driving pressure and the outcome is detected, all subsequent analyses will include non-linear version of driving pressure. The non-linearity assumption will also apply to all other continuous variables across all analyses where appropriate.

If time to mortality is available, we will summarize the time to death (overall survival) as a survival endpoint using survival analysis approach: Kaplan-Meier curves to depict the pattern of survival over time and Cox proportional hazards model to assess the association between driving pressure and death adjusting for all relevant variables as done in the multivariable logistic model described above.

To address the second objective, the multivariable logistic regression model for 30-day mortality will include tidal volume in mL per kg of ideal body weight as well as its interaction with driving pressure, along with potential confounders. A significant interaction term will indicate that the relationship between tidal volume and 30-day mortality is moderated by driving pressure. The varying impact of the interaction between tidal volume and driving pressure on the probability of the primary outcome may be described graphically using quantiles of driving pressure.

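### Two conflicting windows define the exposure medians; one of them, and the confounder intubation time, is undefined for the supraglottic-airway patients the protocol plans to compare

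*Protocol*

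**What the plan says.** **Window, first statement.** Protocol, Exposure Variables, defines Case Start by a ranked list that opens with "Anesthesia Induction End (Concept 50005). If not available, then" and continues through induction begin, procedure start, patient in room and anesthesia start. Case End is extubation, with procedure end, out of room and anesthesia end as fallbacks.

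**Window, second statement.** Protocol, Handling of missing data and artifacts, says of the tidal volume and pressure medians: "Only values between intubation and extubation will be used in these medians". It gives no fallback and does not refer to Case Start or Case End.

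**Supraglottic airways.** Patient exclusion criteria: "Supraglottic airways will be included in the study but examined more closely with secondary statistical analysis as described below". Statistical analysis plans an interaction with driving pressure, followed by subgroup analyses, and its first listed factor is "1) supraglottic air way devices (i.e., LMAs) vs endotracheal tubes".

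**Confounder.** Statistical analysis: "Confounders include but are not limited to age at surgery, gender, intubation time, ventilatory mode, airway device (i.e. endotracheal tube, LMA), pulmonary disease, BMI, ASA". The cover sheet has: "Variables including but not limited to age, gender, intubation time length, pulmonary disease, BMI, and ASA score will be analyzed". Variables to be collected describes the item as "First Intubation time (as minutes", counted from the start of anesthesia, with source "Concept 50695 Categorized note Intubation". The next row collects the last extubation time.

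**Missing data.** Complete-case analysis is used if missingness is not informative, and multiple imputation otherwise.

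**The concern.** The medians in question include the primary exposure. Two programmers working faithfully from this document could therefore derive different driving pressures and different analysis sets. The protocol does not say which window takes precedence.

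The intubation-to-extubation rule also does not fit patients whom the protocol deliberately keeps. A patient managed only with a supraglottic airway has no intubation to open the window. Intubated patients without the relevant time stamp are lost too, although the fallback lists exist for exactly that situation.

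The confounder raises a related problem. Tracheostomies and in-situ endotracheal tubes are excluded, so minutes from anesthesia start to first intubation mostly reflect how long induction took. The cover sheet's wording points to duration instead. The protocol treats duration as relevant: it requires two hours of ventilation so that exposure is long enough to matter for the outcome.

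At stake are the first of three pre-specified effect-modification questions, the reproducibility of the exposure, and the adjustment for duration.

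**Working it through.** **1. The two windows side by side.**

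| | Exposure Variables | Handling of missing data and artifacts |
|---|---|---|
| Start | Induction end, then four fallbacks; none is intubation | Intubation; no fallback |
| End | Extubation, then three fallbacks | Extubation; no fallback |
| Intubated, both stamps present | Defined | Defined; similar window, different start |
| Intubated, a stamp missing | Defined through fallbacks | Undefined |
| Supraglottic airway only | Defined | Undefined as worded |

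**2. Consequence for the interaction if the second window governs.** Supraglottic patients have no observed median driving pressure.
- Under complete-case analysis the airway-device variable is left with one level, so neither its main effect nor its interaction can be estimated.
- Under multiple imputation the exposure would be imputed for the whole group, with no observed supraglottic exposure behind it.

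**3. The confounder.** As a time point (minutes to first intubation) it has no value for a supraglottic case. As a length (intubation to extubation) it also has none. So even if the Case Start to Case End window governs the exposure, complete-case analysis would drop these patients through the covariate, and imputation would supply a value for an event that did not occur.

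**4. Effect on overall power.** Inputs from Power analysis: n = 85,000, event rate p = 0.10, alpha 0.05, power 95%, R² = 0.3. The sides of the test are not stated; two-sided is the choice that reproduces the stated figure. The formula for a continuous covariate in logistic regression, solved for the detectable effect b, is

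b = (z₀.₉₇₅ + z₀.₉₅) / √[n · p(1−p) · (1−R²)]

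Stated case: (1.960 + 1.645) / √(85,000 × 0.09 × 0.7) = 3.605 / √5,355 = 0.0493. The protocol gives 0.049, so its figure reproduces.

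The documents give no supraglottic share. Taking an assumed range and removing all such patients:

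| Assumed share | Patients lost | n left | Detectable b | Power at b = 0.049 |
|---|---|---|---|---|
| 0% | 0 | 85,000 | 0.0493 | 94.8% |
| 1% | 850 | 84,150 | 0.0495 | 94.6% |
| 5% | 4,250 | 80,750 | 0.0505 | 93.8% |
| 10% | 8,500 | 76,500 | 0.0519 | 92.5% |
| 20% | 17,000 | 68,000 | 0.0551 | 89.4% |

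Intubated cases lost for want of a time stamp would come on top. The documents give no rate for these; the same formula applies to any total loss.

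**The case against.** The strongest reply is that this is a wording conflict and not a fatal rule. The section that formally defines the exposure supplies a window that works for both devices. The contrary sentence sits in a paragraph on artifact cleaning and may be loose shorthand for the ventilated period. Reading it as overriding sets it against the sections that include these patients, adjust for their device and plan their comparison.

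That reply defeats three stronger conclusions a reader might draw:

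- **That all supraglottic patients certainly drop out and the subgroup cannot be analysed.** The Case Start to Case End window may be the one applied, and loss through the covariate follows only under complete-case analysis. The documents also do not say how supraglottic placement and removal are recorded under the intubation and extubation concepts. Extubation is the first-choice Case End for every case, supraglottic included.
- **That the primary model adjusts for minutes to intubation.** The table lists variables to collect, not model terms. Extubation time is collected, so a length could be derived. Surgery duration is also collected, and the confounder list is open-ended.
- **That the primary analysis is seriously underpowered as a result.** The table above does not show this for the assumed shares.

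What remains is the conflict itself. The word only is restrictive, and nothing gives the other window precedence. Multiple imputation is no remedy for a quantity that does not exist. Deriving a length from intubation and extubation would still leave supraglottic patients without a value. This is also not detail that a protocol may leave to an analysis plan: two stated rules disagree, and one conflicts with a planned comparison.

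**Conclusion.** The point holds as a conflict to be resolved before the data are derived. The protocol states two incompatible windows for the primary exposure, and one is undefined for a group it includes and plans to compare. If that window governs, supraglottic patients and intubated cases lacking a time stamp lose the exposure, and the airway-device interaction cannot be estimated from observed data. Intubation time is inconsistently defined and, in either form, has no value for a supraglottic case.

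This rests on reading intubation literally, so that supraglottic placement does not count as one. The number affected is unknown. Overall power changes little: the detectable effect rises from 0.0493 to between 0.0495 and 0.0551 if 1% to 20% of patients are lost, and those shares are assumptions. The harm falls on the pre-specified airway comparison and on adjustment for duration.

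**What to change.** 1. Use the Case Start to Case End window in Exposure Variables, limited to minutes of positive-pressure ventilation, for all tidal volume and pressure medians.
2. In Handling of missing data and artifacts, replace the intubation-to-extubation sentence with a reference to that window.
3. In the confounder list and on the cover sheet, replace intubation time with duration of ventilation, defined as ventilated minutes in that window for both airway devices.

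The cost is a few wording changes and one variable derived from data already requested. For some cases the fallback time stamps bound the ventilated period less exactly than intubation and extubation would; the restriction to ventilated minutes limits this. Because the fix relies on that restriction, its definition should be confirmed at the same time: the text at hand gives the condition as PIP minus PEEP of at most 6.
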